Outcome measures: Venous patency, blood flow direction, peak reflux velocity, circumferences (C1, C2) at the end of each segment length (L), BMI, VRT, Genomic DNA blood test, Estriol (E3) levels, progesterone serum levels, outcome of quality of life.

Population: 70 Random pregnant women.

Eligibility: Pregnant women aged between 18-47 years old.

Duration: 1 year, follow up period will be conducted at the end of first, second and third trimester and three months after giving birth.

1 Introduction

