3.3.2 Protocol for Duplex ultrasound scan (DUS)

All recruited pregnant women be scanned by duplex ultrasound scan (DUS) to investigate the evidence of VV. The examination will be bi lateral for each patient. The patient will be asked to remove their clothes to expose the lower limb from groin to ankle. Patient will be examined standing to evaluate valves competency against gravity. This is because veins are more dilated while standing which make it easier and more accurate to assess. This examination is considered intimate; therefore, a chaperone will be offered. The scan duration will take 30-45 min and patients may sometimes feel dizzy during the examination. To overcome this issue, patients will be asked to sit and take a rest during the examination.

There are two main techniques which will be applied to all venous segments. Firstly, B mode technique. B mode technique will be used to evaluate vein patency in transverse scan plane by observing the compressibility of veins to rule out any possibility of blood clots. Secondly, Spectral (Pulse wave) doppler technique will be used to evaluate venous flow characteristics (phasicity, spontaneity and direction flow) in longitudinal scan plane by applying manual distal augmentation to assess the reflux duration. All scans and measurements will be performed on SuperSonic Imagine's Aixplorer ® ultrasound system. Following this, 9 MHz linear ultrasound probe will be placed on the patient skin over the venous blood vessel to be scanned, with the use of coupling gel between the skin and the probe.

The scan will start by evaluating the deep and superficial veins system. Firstly, deep veins will be assessed by scanning the Common femoral vein (CFV) at the groin for patency and flow. Any abnormality in CFV indicates iliac vein obstruction therefore iliac veins and inferior vena cava should be examined. The examination will be continued by scanning the length of femoral vein (FV) (proximal to distal), popliteal vein and calf veins. Any thrombus or incompetence (Incompetent veins are defined as a reflux time more than 0.5 seconds) will be recorded.

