7.2 Study outcome measures

	Intervention/procedure	Outcome measures
Primary outcome	DUS	
 • Patency • Blood flow direction(antegrade/retrograde) • Peak reflux velocity
Secondary outcomes	VFI	
 • Patency • Blood flow direction(antegrade/retrograde) • Peak reflux velocity
	Truncated cone tool	
 • C1 • C2 • h
	PPG	Severity of venous reflux by measuring Venous refiling time (VRT) (Abnormal less than 20 sec)
	Genomic blood test	Genomic DNA
	Hormonal Blood test	Estroil (E3) levels, progesterone serum levels
	AVVQ questionnaire	Outcome of quality of life (0-100). 0 least severe (good quality of life), 100 most severe (low quality of life).

8 Statistics and data analysis

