8.2 Analysis plan

All analyses will be performed based on the intention of follow-up. The analysis population will include all participants enrolled in the study, including those who developed varicose veins during pregnancy and those who do not.

Analysis of primary and secondary outcomes:

Venous patency and Peak reflux time recordings from VFI scan will be correlated with Venous patency and peak reflux time recordings from DUS scan. This will be performed using descriptive summary statistics. Mixed multivariable logistic regression will be used to model venous patency and peak reflux velocity in each scan.

Secondary outcome which include measuring the circumferences (C1, C2) and length of segments (h) using Truncated cone method. Calculated volume will be determined by summing segment volumes derived from the truncated cone formula. Pearson product moment correlations, paired t tests, and linear regression tests will be used to assess relative association and absolute differences between calculated volumes in each follow up.

Secondary outcome which include PPG will be analysed by comparing the mean value for the venous refilling time (VRT) by Student's *t* test, agreement between DUS and PPG classification was expressed as a kappa (**K**) value.

Genomic DNA blood samples results will be correlated with the UK biobank study. Test statistics will be used to identify genetic variants that influence varicose vein susceptibility.

Each hormonal blood samples results including Estroil (E3) and progesterone serum levels will be correlated with the results of the next follow up to provide comprehensive information about increased hormonal levels in pregnancy and varicose veins development.

Outcome of quality of life statistical analysis will be performed using the Statistical Package for the Social Sciences (SPSS 23.0) for Windows. Evaluation of AVVQ consisted of quality of life in first trimester, second trimester, third trimester and three months after giving birth will be done using the Friedman test.

8.3 Data analysis:

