The data obtained will be subjected to statistical analysis by an independent biostatistician. SPSS Version 23.0 or/ and STATA Version 10.0 will be used for statistical analysis. Measures such as the mean and standard deviation or median and interquartile range will be used to summarise continuous variables such as age and BMI. Tables reporting the numbers and percentages will be used for categorical variables such as varicose veins and smoking. Chi square or Fisher's exact test will be used to compare categorical variables such as varicose veins and smoking at the final trimester. The t-test or Mann-Whitney test will be used to compare continuous variables such as age with varicose veins at the final trimester. The paired t-test or Wilcoxon signed-rank test will be used to compare BMI between first and third trimester. The Kappa statistic will be used to compare DUS and VFI regarding direction and velocity. Longitudinal analysis will be used to look at factors associated with varicose veins. Factors include age, BMI, smoking, ethnicity, pregnancies and family history. A significance value (p-value) less than 0.05 is considered statistically significant.

9 Regulatory issues

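### Peak reflux velocity, a continuous primary DUS measure, is assigned to logistic regression (8.2) and kappa (8.3) with no cut-point or bands, and 8.2 mixes it with reflux time

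*Combined protocol and SAP*

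**What the plan says.** - **Outcome.** Section 7.2 puts "Peak reflux velocity" in the primary row under DUS, with patency and flow direction, and repeats it as a secondary measure under VFI. Direction is given two categories; velocity is given none. The study summary also lists velocity among the outcome measures and does not list reflux time.
- **Model.** Section 8.2: "Mixed multivariable logistic regression will be used to model venous patency and peak reflux velocity in each scan".
- **Comparison of scans.** Section 8.3: "The Kappa statistic will be used to compare DUS and VFI regarding direction and velocity". VFI is secondary in 7.2, so this is a secondary method comparison.
- **Reflux time.** Just before the regression sentence, 8.2 says "Peak reflux time recordings from VFI scan will be correlated with Venous patency and peak reflux time recordings from DUS scan", and adds "This will be performed using descriptive summary statistics". Reflux time is not an outcome in 7.2.
- **Scan procedure.** In 3.3.2 the Doppler step is done "by applying manual distal augmentation to assess the reflux duration", and the only ultrasound reflux threshold is a duration: "Incompetent veins are defined as a reflux time more than 0.5 seconds".
- **Purpose of VFI.** Section 3.3.3 presents VFI as the answer to spectral Doppler's limited estimation of peak reflux velocity.

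**The concern.** Velocity is a continuous quantity. Ordinary logistic regression and kappa both work on categories, and the plan defines none for velocity. Two things are at stake.

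For the primary measure, whoever runs the model must choose a cut. If that happens after the data are seen, the result can depend on the choice, and any cut discards information.

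For the secondary comparison, the useful question is how far the two methods differ in cm/s, because VFI is offered as the better velocity estimate. Kappa does not answer that, and its value depends on bands that are not stated.

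The change of wording between time and velocity in 8.2 also leaves unclear which quantity each analysis uses.

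**Working it through.** **1. The plan's own figures.** The documents give no velocity mean, SD, cut-point or band, so there is no velocity figure to reproduce. The power in 8.1 is for a proportion and does not use velocity.

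**2. Which quantity is meant?**

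| Place | Quantity named |
|---|---|
| Study summary | velocity |
| 3.3.2 (DUS) | reflux duration; incompetence above 0.5 s |
| 3.3.3 (VFI) | duration for conventional Doppler; velocity for VFI |
| 7.2 | velocity, under both DUS and VFI |
| 8.2, comparison of scans | reflux time |
| 8.2, regression | velocity |
| 8.3, kappa | velocity |

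If the regression sentence means time, the 0.5 s rule supplies the binary outcome and step 3 does not apply. If it means velocity, no rule exists.

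**3. Information kept if velocity is cut (regression, 8.2).** Assume a normal velocity in refluxing veins, independent veins and small effects. Relative to the continuous analysis, a cut at quantile p keeps φ(z_p)² / [p(1 − p)], where φ is the standard normal density. No mean or SD is needed.

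- Median: 0.3989² / 0.25 = 0.637
- 25th or 75th percentile: 0.3178² / 0.1875 = 0.539
- 10th or 90th percentile: 0.1755² / 0.09 = 0.342

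**4. Kappa and the choice of bands (8.3).** All inputs are assumptions. DUS velocity X is normal with mean 25 and SD 8 cm/s. VFI velocity is Y = X + a normal difference with mean 0 (no bias) and SD d. Band edges lie at multiples of 5 or 10 cm/s. Unweighted κ = (p_o − p_e) / (1 − p_e), where p_o is observed and p_e chance agreement, by numerical integration. At d = 2:

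- 5 cm/s bands: (0.683 − 0.171) / (1 − 0.171) = 0.62
- 10 cm/s bands: (0.841 − 0.327) / (1 − 0.327) = 0.76
- Split at 25: (0.922 − 0.5) / (1 − 0.5) = 0.84

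The assumed d matters a great deal, so it is varied:

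| Difference SD (cm/s) | 5 cm/s bands | 10 cm/s bands | Split at mean |
|---|---|---|---|
| 1 | 0.81 | 0.88 | 0.92 |
| 2 | 0.62 | 0.76 | 0.84 |
| 4 | 0.34 | 0.54 | 0.70 |
| 6 | 0.19 | 0.36 | 0.59 |

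As a check, the split at the mean has the closed form κ = (2/π)·arcsin(ρ), with ρ = 8/√(64 + d²). At d = 6, ρ = 0.8 and κ = 0.59.

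Each row describes one set of data, and only the bands change. The gap from finest to coarsest is 0.11 at d = 1 and 0.40 at d = 6.

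**5. Bias against scatter.** Split at 25 cm/s, a 5 cm/s bias with d = 2 gives κ = 0.54, with discordant cells of 22.8% and 0.0%. No bias with d = 7.0 also gives 0.54, with 11.4% and 11.4%. The cross-table shows the direction of disagreement; neither it nor kappa gives its size in cm/s.

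**The case against.** **Velocity may be a slip in 8.2.** The same paragraph opens with reflux time, and 3.3.2 measures duration and defines incompetence by it. On that reading logistic regression is sound and the information-loss point falls away. This is possible, but the summary, 7.2 and 8.3 all say velocity, so it is not the better reading. The text needs correcting either way.

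**A reader might infer that the model cannot be run at all.** That goes too far. A cumulative (ordinal) logistic model can take each distinct velocity as an ordered level with no chosen cut. Section 8.2 does not say ordinal, so the model stays unspecified, but it is not impossible.

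**A reader might infer that nothing in cm/s will be reported.** The documents do not support that. Section 8.3 summarises continuous variables by mean and SD or median and interquartile range, giving age and BMI only as examples, so velocity may be covered. The summaries in 8.2 may cover it too if time there is a slip for velocity. These could give per-scan means, but not limits of agreement.

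**A reader might infer that DUS will not record velocity.** Section 7.2 lists it under DUS, and 3.3.3 starts the VFI scan with conventional pulse-wave Doppler. The inconsistency is one of naming.

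**The sizes are illustrative.** This stands. Section 8.2 specifies a mixed model and does not restrict it to refluxing veins, so 64%, 54% and 34% are not this study's exact loss. The kappas rest on assumed velocities. Mixing weighting schemes would widen their spread, but 8.3 names plain kappa, which is normally unweighted, so only unweighted values are used.

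**Conclusion.** The concern holds as a gap in specification that should be fixed before analysis. As written, a continuous primary measure is assigned to a method for categorical outcomes with no categories defined, and the secondary DUS-VFI velocity comparison uses a statistic whose value depends on unstated bands. Section 8.2 also does not keep reflux time and reflux velocity apart.

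The regression part depends on velocity being the intended outcome. If so, a binary cut keeps roughly a third to two thirds of the information, assuming normal velocity, independent refluxing veins and small effects. The kappa part does not depend on how 8.2 is read, because 8.3 names velocity itself. At an assumed mean of 25 and SD of 8 cm/s with no bias, the choice of bands alone moves kappa by 0.11 to 0.40 as the difference SD goes from 1 to 6 cm/s.

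The sample size in 8.1 is unaffected, and nothing here faults logistic regression for patency or kappa for flow direction.

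**What to change.** 1. **Section 8.2.** Keep mixed logistic regression for patency and for incompetence as defined in 3.3.2. Analyse velocity as continuous, with a linear mixed model in refluxing veins or a two-part model (reflux yes/no, then velocity where present), transformed if skewed.
2. **Section 8.3.** Keep kappa for flow direction. For velocity, report Bland-Altman bias and limits of agreement in cm/s in veins with reflux on both scans, allowing for repeated limbs and visits.
3. **Wording.** Reconcile 3.3.2, 3.3.3, 7.2, 8.2 and 8.3 so that reflux time and reflux velocity are named consistently.

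If a categorical velocity is still wanted, fixing the cut-point, bands and kappa weights before analysis would cure the missing definition, but not the loss of information or the lack of a difference in cm/s.

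The cost is a protocol/SAP amendment and slightly more analysis work, with no added visit or scan. Velocity estimates will be less precise because only refluxing veins contribute.

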3.3.4 Protocol for Limb volume assessment

Weight gain during pregnancy is well known. This occurs not only due to fetal growth and uterus enlargement, but also due to water retention and increased blood volume which are required for fetal circulation. This excessive water retention especially in the third trimester is coupled with accumulated fat cause swelling (oedema) especially in both lower limbs. Therefore, measuring limb volume during pregnancy is considered significant to estimate water and fat amounts gained during pregnancy and correlate these findings with potential VV incidence. This proposed study will assess the lower limb volume based on girth measurements using Truncated cone method. This method has the advantage of measuring bilateral limb volume oedema where no comparator (unaffected) limb is available. This method measures limb volume by manual perimetry using tape measure to find limb circumference. Tape measure tension may be inconsistent which can change the limb circumference measurement by up to 3% (Cheah *et al.*, 1989). Therefore, this study will use spring-loaded controlled tension device to keep the tape in closer contact with the skin without compressing the underlying tissue.

Measurements will be taken while the patient is standing. Circumferences will be measured every 10 cm from the sole up to the seventh measurement. A single researcher will measure all patients to prevent differences in tension on the tape. The data will be processed using the truncated-cone formula (Campanholi, Duprat Neto and Fregnani, 2011):

$$V = h (C1 \times C2 + C1^2 + C2^2) / 12\pi$$

V: Volume of each segment (final segment of the limb).

C1 and C2: Circumference measured between the points (at either end of each segment length)

H: Distance between the circles (C1 and C2 in each segment), measured in centimetres.

Total limb volume: is determined by the sum of the segment volumes.

Finally, Patient will be asked to rest and take a seat on a chair, circumferential measurements will be entered into computer software programmes or pre-programmed calculators to calculate limb volume of each recruited patient.

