8.1 Sample size

An exact binomial test with a nominal 5% two-sided significance level will have 91.27% power to detect the difference between the null hypothesis proportion, π_0 of 0.25 and the Alternative proportion, π_1 , of 0.1 when the sample size is **70**.

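### Limb volume is meant to be related to varicose veins (VV), but the plan only compares one total volume between visits and never relates its change to VV

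*Combined protocol and SAP*

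**What the plan says.** Section 3.3.4 gives the purpose of the measurement: "to estimate water and fat amounts gained during pregnancy and correlate these findings with potential VV incidence". The same section places the swelling in both lower limbs and counts fat as well as water. On method it says: "Circumferences will be measured every 10 cm from the sole up to the seventh measurement". Each segment is treated as a truncated cone, and total limb volume "is determined by the sum of the segment volumes". It does not say whether the first level is at 0 or 10 cm. One researcher takes all measurements with a tension-controlled tape.

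Section 7.2 lists the truncated cone measurements as a secondary outcome. Section 8.2 analyses the summed volume: "Pearson product moment correlations, paired t tests, and linear regression tests will be used to assess relative association and absolute differences between calculated volumes" at each follow-up. It defines no change score, segment split or model with VV as outcome, and the linear regression has no stated outcome or covariates.

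Section 8.3 plans a longitudinal analysis of factors associated with VV and lists age, BMI, smoking, ethnicity, pregnancies and family history. Limb volume is not listed. Section 8.3 also has a generic t-test or Mann-Whitney comparison of continuous variables by VV status in the final trimester, with age as the example.

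**The concern.** The stated purpose is a gain, related to VV. The stated analysis compares volumes with each other across visits. It can show that legs get larger on average, but not whether women whose legs gain more are those who develop VV.

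Two features make the gap worse. First, an analyst who looks in the plan for a comparison by VV status finds only the generic final-trimester test. Applied to absolute volume, it would set a small difference in gain against large constant differences in leg size. Second, the only volume defined is a total that reaches above the knee, so a change confined to the lower leg is diluted.

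At stake is a secondary outcome that takes effort at all four visits and could end without answering its own question, or with a null result that reflects leg size rather than the absence of an association.

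**Working it through.** **The plan's own figure.** The only design figure is in section 8.1: "An exact binomial test with a nominal 5% two-sided significance level will have 91.27% power" for "the null hypothesis proportion, π_0 of 0.25" against "the Alternative proportion, π_1 , of 0.1", "when the sample size is 70". It reproduces. The largest k with P(X ≤ k | 70, 0.25) ≤ 0.025 is k = 10 (tail 0.0220), and P(X ≤ 10 | 70, 0.10) = 0.9127. It does not concern limb volume. It is used here only for n = 70 and for plausible numbers with VV: 0.10 × 70 = 7, and 0.25 × 70 = 17.5, taken as 17.

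**Inputs the documents do not give (assumptions).** Between-woman CV of volume 15-20%; SD of within-woman change 3-5% of volume; difference by VV status 3% of volume; girths 22, 27, 35, 37, 42, 50 and 56 cm at 10 to 70 cm.

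**1. Between-visit Pearson correlation.** If follow-up volume is first-visit volume plus an independent change, r = CV / √(CV² + SD²).
- CV 15%, SD 5%: 0.15 / √(0.0225 + 0.0025) = 0.949.
- CV 20%, SD 3%: 0.20 / √(0.04 + 0.0009) = 0.989.

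The mean gain does not appear in the formula. Adding the same volume to every leg leaves r unchanged.

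**2. Paired t test.** Each woman's constant leg size cancels. For a mean shift of 2.3% in total volume, the noncentrality is 0.023 / (SD / √70): 6.41 at SD 3% and 3.85 at SD 5%. Two-sided 5% power is about 100% and 97%.

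**3. Comparison by VV status.** Two-sample t test with 68 df and noncentrality 0.03 / (SD × √(1/n₁ + 1/n₂)):

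| VV v no VV | Absolute volume, SD 15% | Absolute volume, SD 20% | Change, SD 3% | Change, SD 5% |
|---|---|---|---|---|
| 7 v 63 | 8% | 7% | 70% | 32% |
| 17 v 53 | 11% | 8% | 94% | 56% |

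A separate simulation in millilitres gave the same picture. With 18 of 70 women with VV, 200 ml extra gain, between-woman SD 1000-2000 ml and SD of change 200-400 ml, power was 6-11% on absolute volume and 43-96% on change.

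**4. What the total contains.** The formula in 3.3.4, V = h(C1·C2 + C1² + C2²)/12π, is the correct truncated cone. Seven levels give six segments.
- *Levels 10-70 cm:* 479, 769, 1032, 1243, 1688 and 2238 ml, total 7449 ml. The share above 40 cm is (1243 + 1688 + 2238) / 7449 = 69%. Three other assumed profiles gave 65-69%. A 3% rise in girth at the four lowest levels adds 6.1% to the 10-40 cm volume but 2.3% to the total. A 2% rise at the three highest levels adds 2.5% to the total.
- *Levels 0-60 cm*, same girths, with an assumed 22-28 cm at the lowest level: the share above 40 cm is 51-52%. The same 3% rise at 10-40 cm adds 3.3% to the total, and a 2% rise at 50-60 cm adds 1.7%.

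The total dilutes below-knee change under both readings. The amount, and which part of the leg moves the total more, depend on where the first level lies.

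**The case against.** The strongest reply is that the sentence in 8.2 also plans paired t tests and linear regression. The paired test is a within-woman analysis of absolute change, so leg size does not affect it, and step 2 shows ample power even for a diluted shift. This stands. A reader might infer that leg size swamps the whole limb-volume analysis; the documents do not support that. The Pearson correlation is one of three methods and can describe relative association, provided it is not read as evidence about swelling.

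A reader might also infer that lower-leg swelling is the study's target and that thigh fat contaminates it. Section 3.3.4 does not say so: it names fat as well as water, and both lower limbs. Nor can the total be called mostly thigh without qualification. With levels at 10-70 cm, the 40-50 cm segment may be largely knee, and only 53% of the volume lies above 50 cm. With levels at 0-60 cm that share is 30%, and the comparison of lower-leg and upper-leg changes reverses.

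Finally, the low power on absolute volume belongs to an analysis that 8.3 does not explicitly assign to limb volume. That is correct, so the figure is conditional. The underlying gap is not: no other analysis by VV status is specified for volume. Unspecified linear regression does not fill it, and change or segment volumes derived after the data are seen would not be prespecified.

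**Conclusion.** The concern holds in a limited form. Section 3.3.4 promises to relate volume gained to VV, and neither 8.2 nor 8.3 contains an analysis that does so. Mean gain over time is adequately covered by the paired t test.

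The cost of falling back on absolute volume is large under the stated assumptions: 7-11% power against 32-94% for within-woman change. The direction rests on women differing in leg size far more than a leg changes. The exact figures rest on assumed SDs, an assumed 3% difference and 7 or 17 women with VV.

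Dilution by the total is real but less certain, with about 52-69% of the volume above 40 cm depending on the first level and the assumed girths. No tape volume, split or summed, can separate water from fat. This is an inexpensive improvement to a secondary outcome and does not affect the primary analysis.

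**What to change.** In section 8.2:
- Prespecify within-woman change in limb volume from the first-trimester visit, as percent change or as follow-up volume adjusted for first-visit volume. Either is acceptable; choose one in advance. Use the same levels for a given woman at every visit.
- Report the volumes below and above 40 cm separately, alongside the total.
- Keep the paired t test for mean gain. Do not use the between-visit Pearson correlation as evidence about swelling.

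In section 8.3, add change in limb volume to the factors in the longitudinal VV analysis, allowing for two legs per woman.

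In section 3.3.4, state whether the first level is at 0 or 10 cm, and reword the purpose so that it does not claim that tape measurements separate water from fat.

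The cost is wording and a few more volumes to report. All the circumferences needed are already recorded.

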3.3.5 Protocol for Iliac vein compression test (venous outflow function)

This proposed study will examine iliac vein compression (venous outflow function) in pregnancy using photoplethysmography (PPG) technique. This is due to the difficulty of examining iliac veins using ultrasound in pregnancy due to increased size of gravid uterus. Large size of gravid uterus in pregnancy causes iliac veins compression which makes iliac veins hard to investigate. PPG is a non-invasive method used to evaluate the severity venous reflux by measuring the venous refilling time (VRT). VRT is considered to be abnormal when the refilling time is measured (less than 20 seconds). PPG technique has low specificity compared to other imaging tests and it is considered not accurate in locating the areas of reflux. However, alongside with its capability of evaluating the degree of reflux, it can also predict the treatment outcomes (Cheng and Wong, 1995).

The principal of PPG works by using a small light source and a photoelectric cell attached to the skin. Produced light will transmit the skin and will be scattered by the tissue and partially absorbed. Scattered light will emerge out passing the skin to be detected by photoelectric cell. Photoelectric cell will be attached on the side or opposite the source of light to monitor blood perfusion based on transmission and reflection modes. Following this, the intensity of the light signals detected by photoelectric cell will be converted to PPG signals.

In this proposed study, patient will be seated with her both legs dangling on the floor. PPG sensor will be attached to the patient's skin in the medial supramalleolar area of the leg (the distal lower medial area of the leg). The exam will start by asking the patient to flex and extend one foot (five times), while the other foot placed on the floor.

Following this, a traced graph will appear on the machine's screen. When the trace is stable, it means that it is the end of the VRT. The exam will be repeated to evaluate the filling time of the second leg. All measurements will be recorded immediately.

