5.2.2 Serious AEs

An SAE form should be completed and faxed to the Chief Investigator within 24 hours. However, death due to eclampsia and any health complications worsened during pregnancy does not need reporting as SAEs.

All SAEs should be reported to **the North of Scotland Research Ethics Committee** where in the opinion of the Chief Investigator, the event was:

- 'related', ie resulted from the administration of any of the research procedures; and

- 'unexpected', ie an event that is not listed in the protocol as an expected occurrence

Reports of related and unexpected SAEs should be submitted within 15 days of the Chief Investigator becoming aware of the event, using the NRES SAE form for non-IMP studies. The Chief Investigator must also notify the Sponsor of all SAEs.

Local investigators should report any SAEs as required by their Local Research Ethics Committee, Sponsor and/or Research & Development Office.

Contact details for reporting SAEs

[contact]

[contact]

[contact] attention [name]

[contact] (Mon to Fri 09.00 – 17.00)

6 Incidental findings:

A lay summary of aggregated results will be provided to all participants. If there is an incidental finding such as DVT, which likely have a major impact on patient's medical management then the doctor treating her will be informed and participant will be removed/ withdrawn from the study.

7 Assessment and follow up

All previously mentioned interventions and procedures including (DUS, VFI, Truncated cone tool, PPG, hormonal blood test, AVVQ questionnaire) will be performed four times (in first, second, third trimester once and three months after giving birth). DNA genomic blood test will be performed once only in the first trimester of pregnancy. No

further follow-up required after this time point. The study expected time for each participant is 12 months in total.

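### Section 8.2 names an ordinary Student's t test for VRT, which is read on two legs at four visits in the same women, and states neither the contrast nor the unit of analysis

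*Combined protocol and SAP*

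**What the plan says.** The analysis of VRT is one sentence in Section 8.2. PPG "will be analysed by comparing the mean value for the venous refilling time (VRT" by Student's t test, and "agreement between DUS and PPG classification was expressed as a kappa" value. The sentence does not say which groups or visits are compared, whether the leg or the woman is the unit, or how repeats are handled.

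The data are repeated in two ways:
- **Legs.** Section 3.3.5 tests one leg and then the other: "The exam will be repeated to evaluate the filling time of the second leg". The duplex scan it is compared with is also two-sided (Section 3.3.2: "The examination will be bi lateral for each patient").
- **Visits.** Section 7 says the procedures, PPG among them, "will be performed four times (in first, second, third trimester once and three months after giving birth".

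Elsewhere the plan names methods for dependent data. Section 8.2 has paired t tests for limb volume and the Friedman test for AVVQ. Section 8.3 states: "The paired t-test or Wilcoxon signed-rank test will be used to compare BMI between first and third trimester". The mixed logistic model in Section 8.2 covers patency and peak reflux velocity. The longitudinal analysis in Section 8.3 covers factors associated with varicose veins, and VRT is not listed among them.

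**The concern.** With 70 women, two legs and four visits there are up to 560 VRT readings, but only 70 independent units. A two-sample t test treats every value as independent. If it is given the repeated readings, its standard error is wrong, and the direction depends on the contrast. Comparing visits without pairing leaves the between-woman variation in the error term, so real change over pregnancy may be missed. Comparing women with and without VV while counting legs or visits as separate women makes the standard error too small, so chance differences are declared significant too often.

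PPG is the study's chosen test of venous outflow, because Section 3.3.5 says the iliac veins are hard to examine by ultrasound in pregnancy. It therefore bears directly on the secondary aim about mechanical factors, and Section 8.3 declares significance at p below 0.05.

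**Working it through.** **The plan's own figure.** Section 8.1 states 91.27% power for an exact binomial test (0.25 v 0.10, n = 70, 5% two-sided). With 0.025 in the lower tail the test rejects at 10 or fewer of 70. Its lower-tail size is 0.0220 and its power at 0.10 is 0.9127. The figure is reproduced, and it does not involve VRT.

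**Inputs.** 70 women (study summary), 2 legs (Section 3.3.5), 4 visits (Section 7), alpha 0.05 (Section 8.3). The within-woman correlation of VRT is not in the documents. I assume 0.3, 0.5 and 0.7.

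**A. Two visits compared by an unpaired t test, one leg.** With correlation r between visits, true SE / naive SE = √(1 − r). Take the effect at which a paired test has 80% power, a standardised shift of 1.96 + 0.84 = 2.80. The unpaired test's power is then Φ(2.80 − 1.96/√(1 − r)).

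| r | true/naive SE | interval too wide by | true type I error | power (paired 80%) |
|---|---|---|---|---|
| 0.3 | 0.84 | 1.2 | 1.9% | 68% |
| 0.5 | 0.71 | 1.4 | 0.6% | 51% |
| 0.7 | 0.55 | 1.8 | 0.04% | 22% |

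**B. Women with and without VV compared, readings entered as independent.** If VV status is the same for all m readings from a woman, the design effect is 1 + (m − 1)ICC, and the true type I error is 2[1 − Φ(1.96/√(design effect))].

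| ICC | m = 2: design effect | type I error | m = 8: design effect | type I error |
|---|---|---|---|---|
| 0.3 | 1.3 | 8.6% | 3.1 | 27% |
| 0.5 | 1.5 | 11.0% | 4.5 | 36% |
| 0.7 | 1.7 | 13.3% | 5.9 | 42% |

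At ICC 0.5 the 560 readings carry the information of about 560/4.5 = 124.

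**C. How far B depends on shared status.** By simulation at ICC 0.3 to 0.7:
- Both legs at one visit, leg status independent within a woman: about 5%, so no inflation.
- Both legs at one visit, disease only ever on one side: about 4%, slightly conservative.
- Eight readings pooled, onset at a random visit: about 21%, 28% and 34% if status belongs to the woman, and about 12%, 16% and 18% if it belongs to the leg.

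**D. Uses of the t test that are valid.** One value per woman (the mean of her readings, or one leg at one visit) in a between-women test gave 4.7% to 5.4% type I error in simulation. A paired test between visits on one leg gave 4.3% to 4.9%. Pairing visits by leg but counting the two legs as independent gave 6.7% to 8.8%, so pairing alone does not deal with the second leg.

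**E. Kappa.** On 560 simulated leg-visits the mean kappa was 0.516 with no clustering and 0.512 at latent correlation 0.7, so the estimate hardly moves. An ordinary large-sample 95% interval, if one were attached, would cover 92.5%, 88.5% and 81.2% at latent correlations 0.3, 0.5 and 0.7.

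**The case against.** The strongest reply is that the plan does not commit to a faulty use. Student's t test can loosely include the paired form, and an analyst could average each woman's readings first. Both routes hold about 5%, as D shows. That stands as a limit on the claim. But the plan writes the word paired where it means it, for limb volume and BMI, and nothing in it directs averaging or a single leg.

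Four stronger readings are tempting, and the documents do not support them.

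- **That the error bars are wrong whichever contrast is used.** They are not. Besides the valid uses in D, an unpaired comparison of two visits using both legs has true/naive variance 1 + (between-leg correlation) − (same-leg plus cross-leg correlations between visits). With 0.6, 0.3 and 0.3 this is 1 + 0.6 − 0.6 = 1, exactly nominal. In the settings simulated, type I error for this contrast was 0.7% to 1.9%.
- **That the t test is valid only if most of the data are discarded.** The mean of all eight readings uses every value and is valid.
- **That 27% to 42% is what the study should expect.** No section says readings will be pooled over visits. The general two-group comparison of continuous variables in Section 8.3 is set at the final trimester, although its example is age and so does not settle VRT. Section 8.2 also expects some women to develop varicose veins during pregnancy, so status changes over visits and the inflation is smaller (C).
- **That the planned kappa is wrong.** Only a kappa value is promised, with no interval or test, and the value itself is barely affected (E).

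**Conclusion.** The concern holds as a SHOULD-level point. Section 8.2 names an ordinary t test for data repeated over two legs and four visits, gives no contrast or unit, and no other section supplies a paired or clustered method for VRT. The plan therefore permits two analyses with opposite faults: serious loss of power for change between visits, and inflated type I error for women with v without VV. The between-women figures are an upper end that applies when status is common to all of a woman's readings. They are smaller or absent when it differs between legs or changes over visits.

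All sizes rest on assumed correlations. The directions in A and B need only a positive correlation and, for B, shared status. VRT is one of several secondary outcomes, and the sample-size statement is untouched.

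**What to change.** In Section 8.2:

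1. State the VRT contrast or contrasts, the visits they use, and whether the unit is the leg or the woman.
2. Replace the Student's t test with a linear mixed model for VRT, on the log scale if skewed. Use fixed effects for visit, VV or reflux status and their interaction, and random effects for woman and for leg within woman. Add a woman-by-visit random effect, or average the legs at each visit, so that the correlation between two legs read on the same day is covered.
3. Report the DUS-PPG kappa per visit at leg level. If an interval is given, obtain it by a bootstrap that resamples women.

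The cost is SAP wording and slightly more analysis. No new data are needed, and the plan already names a mixed model for other outcomes. If a simpler analysis is preferred, one stated value per woman for group comparisons and a paired test on a stated leg for visit comparisons would also be valid.
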